9.9 Good Clinical Practices and Ethical Study Conduct

The study procedures outlined in this protocol will be conducted in accordance with applicable ICH Guidelines, including ICH E6: Good Clinical Practices. As this study is conducted under a US IND, the investigator will also ensure that the basic principles of “Good Clinical Practice”, as outlined in 21 CFR 312, subpart D, “Responsibilities of Sponsors and Investigators”, 21 CFR, part 50 and 21 CFR, part 56 are adhered to.

The study procedures outlined in this protocol will also be conducted in accordance with the principles of the Declaration of Helsinki.

9.10 End of Study Notification

The Sponsor will notify appropriate regulatory authorities and the IRB or EC within 90 days from the end of the clinical study. The end of the clinical study is defined as the last study visit for the last subject.

9.11 Publication of Results

All publications (e.g. manuscripts, abstracts, oral/slide presentations, book chapters) based on this study or relying on data from this study must be submitted to the Sponsor for review and release before submission for publication. The Sponsor is responsible for final approval of all publications.

9.12 Final Report

A clinical trial summary report will be provided to the appropriate regulatory authorities within one year of the end of the clinical study.

APPENDIX A SCHEDULE OF ACTIVITIES AND ASSESSMENTS

Table 2 Schedule of Visit Activities

Examination	Screening	Mid-Screening ^{1C}	Baseline ¹	Week 1 ^{1C} (± 3 days)	Week 2 (± 3 days)	Week 4 (± 3 days)	Week 6 (± 3 days)	Week 10 (± 7 days)	F/U ²	Early Treatment Discontinuation
Demographics	X									
Informed consent	X									
WI-NRS ³	X	X	X	X	X	X	X	X		
DLQI			X			X		X		X
HADS, ESS			X			X		X	X	X
ECG	X				X	X		X	X	X
Vital signs	X		X		X	X	X	X	X	X
Medical history (and prior medications)	X	X	X							
Physical exam ⁴	X		X		X	X	X	X	X	X
Concomitant medications			X	X	X	X	X	X	X	X
Labs ⁵	X				X			X	X	X
Urine pregnancy test ⁶	X		X			X	X	X	X	X
PK blood draw					X	X		X		
Review of I/E criteria	X	X	X							
IGA PN-A and IGA PN-S			X		X	X		X	X	X
Photography (selected sites)			X					X	X	X
Dispense/review menstrual diary (if applicable)	X		X		X	X	X	X	X	X
Dispense/collect eDiary	X								X	X
eDiary review/compliance ⁷		X	X	X	X	X	X	X	X	
Dispense and/or collect study drug			X		X	X	X	X		X
Review study drug compliance					X	X	X	X		
AEs/SAEs ⁸	X	X	X	X	X	X	X	X	X	X

^{1C}Telephone Contact: The Mid-Screening telephone contact should only occur for subjects who require a washout longer than 2 weeks, at least 15 days prior to the scheduled Baseline visit.

¹All visits and windows should be scheduled based on the Baseline Visit (Day 1)

²The Follow-up (F/U) visit occurs 21-35 days (+ 7 days) after the Week 10 visit or the last dose of study drug for subjects who discontinue study drug early.

³WI-NRS at Screening visit will be collected manually on paper for Inclusion/Exclusion criteria. All subsequent WI-NRS are collected daily via eDiary.

⁴Screening physical exam is complete and includes height and weight; other physical exams are targeted and include weight.

⁵Labs are ideally performed in the morning, particularly at visits with endocrine assessments (including Reproductive Endocrinology for females under 55 at age of consent) at Screening, Week 10 and Follow Up. Iron Studies, serum IgE and Serology labs are done only at Screening visit; endomysial antibody test and other optional studies only performed at Screening;

⁶Female subjects of childbearing potential only. Serum pregnancy test is required for positive or equivocal results

⁷See Table 3 for eDiary assessments

⁸During the period between informed consent and first study drug dose, only SAEs caused by a protocol-mandated intervention will be collected.

Table 3 **Schedule of eDiary Assessments**

An eDiary device is provided to subjects at the Screening visit and collected at the Follow-up visit.

Device	Assessment	Frequency and Duration of Assessment
eDiary	WI-NRS	Once daily from Screening/Mid-Screening visit through the Follow-up visit
eDiary	Dosing	Once daily from Baseline visit through Week 10 visit or study drug discontinuation

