5.6 Study Drug Discontinuation

Subjects should be discontinued from study drug treatment in the following situations:

- A female subject desires to become pregnant at the current time, stops contraception or expels her intrauterine device/implant, or becomes pregnant
- A female subject has new breast findings (e.g. a palpable mass or abnormal mammography, discharge), or has abnormal vaginal discharge or bleeding
- The subject decides to discontinue study drug treatment, or withdraws consent from the study
- The subject receives a strong CYP3A4 inhibitor (See [Appendix B](#))

- Any medical condition that may jeopardize the subject's safety if study drug is continued, in the investigator's and/or Sponsor's opinion; this may include the development of persistently (2 successive occasions) abnormal thyroid function tests (TSH >10, or TSH > 6 with low free T4; TSH <0.1, or TSH < 0.35 with high free T4); abnormal morning prolactin, cortisol, or corticotropin levels; or signs and symptoms of adrenal insufficiency
- Discontinuation is deemed to be in the best interest of the subject, in the investigator's and/or Sponsor's opinion, including evidence that the subject does not meet inclusion/exclusion criteria intended primarily for safety reasons, or a persistent lack of adherence to study procedures

The Sponsor or designee should be contacted within 24 hours of investigator's awareness of any study drug treatment discontinuation. Investigators should make every effort to contact the Sponsor or designee before discontinuing study drug treatment, if possible.

Subjects who discontinue treatment with study drug prior to completing the treatment period will enter a 5-week follow-up period following the last dose of study drug in addition to a Follow-up visit (see [Section 3.1](#), [Section 6.5.10](#)). Every effort should be made for subjects to complete the Follow-up visit after a subject has discontinued from study drug.

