5.7 Prior, Concomitant, and Excluded Therapies

Prior therapies (including over-the-counter medications) used to treat the signs and symptoms of PN within the prior 2 years will be recorded for each subject at the Baseline visit.

Concomitant therapies include any therapies (including over-the-counter medications and bland emollients) used by a subject from initiation of study drug treatment through the follow-up period. A record of all medications used will be maintained for each subject throughout the study. Reported information will include a description of the type of drug, treatment period, dosing regimen, the route of administration, and drug indication. The use of any concomitant medication must relate to the subject's medical history or to an AE, except for vitamins/nutritional supplements, emollient use, and routine preventative immunizations.

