6.1 Efficacy Parameters

6.1.1 *Itch Numeric Rating Scale*

The Itch NRS is a validated, self-reported instrument for measurement of itch intensity. It uses a 24-hour recall period and asks subjects to rate the intensity of their itch on an 11-point scale ranging from 0 (no itch) to 10 (worst itch imaginable). Higher scores indicate greater itch intensity. In this study, the subject is asked to rate the intensity of their *worst* itch (WI-NRS) during a 24-hour recall period; the questionnaire is provided in [Appendix C](#). Initial WI-NRS score collected during Screening visit will be collected on paper. All subsequent WI-NRS assessments will be reported by subject via eDiary. Subjects will record their WI-NRS scores once daily via eDiary at approximately the same time each day (+/- 3 hours) throughout the screening, treatment, and follow-up periods, as outlined in [Appendix A](#). Subjects may be allowed to adjust the timing of eDiary completion within the first week of Screening as needed. Standardized training and instructions will be provided to all subjects prior to eDiary use.

6.1.2 *Investigator's Global Assessment of PN Activity*

The IGA PN-A is an instrument used to assess the overall activity of PN lesions at a given time point, as determined by the investigator. It consists of a 5-point scale ranging from 0 (clear) to 4 (severe), as provided in [Appendix D](#). The IGA PN-A uses clinical characteristics of excoriations, crusting, and/or bleeding as guidelines for the overall activity assessment. The number of pruriginous lesions should not be considered for this assessment. IGA PN-A scores will be captured as outlined in [Appendix A](#). Each assessment during the study must be done by the Principal Investigator (PI) or designee. Every effort should be made to ensure that all assessments for a given subject are done by the same individual throughout the study. However, a change in assessor for a given subject, though not ideal, will not be considered a protocol deviation.

6.1.3 *Investigator's Global Assessment of PN Stage*

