- Perform targeted physical examination, including weight
- Assess and record any AEs and SAEs
- Collect returned study drug
- Utilize IWRS to assign new bottle of study drug
- Review eDiary for compliance, re-train subject as needed
- Confirm next scheduled visit

6.5.9 *Week 10 Visit*

The Week 10 visit occurs 70 days (± 7 days) after the Baseline visit. At the Week 10 visit, the following procedures and assessments are to be performed:

- Ask the subject to complete the DLQI, HADS, and ESS questionnaires
- Assess and record any changes in the subject's concomitant medications
- Female subjects should be queried for presence of new breast masses or abnormal discharge, and abnormal vaginal bleeding or discharge
- Review menstrual diary and record dates of menstrual flow (if applicable)
- Obtain ECG
- Obtain vital signs
- Perform targeted physical examination, including weight
- Perform IGA PN-A
- Perform IGA PN-S
- Perform a urine pregnancy test for females of childbearing potential (with positive or equivocal results confirmed by a serum pregnancy test)

- Draw blood for clinical laboratory tests (morning blood sampling due to Endocrine assessments)
 - Reproductive endocrine labs for females under 55 years of age at consent
 - Endocrine
 - Hematology
 - Chemistry
- Collect PK blood sample
- Assess and record any AEs and SAEs
- Collect returned study drug
- Obtain photos (at selected sites, only subjects that signed photography consent)
- Review eDiary for compliance, inform subject to continue entering WI-NRS score until Follow-up visit
- Review study drug compliance with re-training as required
- Confirm next scheduled visit date

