6.5.10 Follow-up Visit

The required Follow-up visit occurs 21 or 35 (+7 days) after the Week 10 visit or the last dose of study drug for subjects who discontinue study drug early. The required follow-up period is defined as a minimum of 3 weeks for those subjects who will enroll in the one-year open-label safety study on the date of the follow-up visit, and as 5 weeks for those subjects who will not be enrolled in the one-year open-label safety study of serlopitant. Should a subject present for the follow-up visit prior to 5 weeks after the last dose of study drug and be excluded from participation in the one-year study for any reason, the subject will be required to return at 5 weeks after the last dose of study drug for a complete follow-up visit.

At the Follow-up visit, the following procedures and assessments are to be performed:

- Register visit into the IWRS
- Ask the subject to complete the HADS and ESS questionnaires
- Assess and record any changes in the subject's concomitant medications
- Female subjects should be queried for presence of new breast masses or abnormal discharge, and abnormal vaginal bleeding or discharge
- Review menstrual diary and record dates of menstrual flow (if applicable)
- Obtain vital signs

- Perform targeted physical examination, including weight
- Perform IGA PN-A
- Perform IGA PN-S
- Obtain ECG
- Obtain photos (at selected sites, only subjects that signed photography consent)
- Perform a urine pregnancy test for females of childbearing potential (with positive or equivocal results confirmed by a serum pregnancy test)
- Draw blood for clinical laboratory tests (morning blood sampling due to Endocrine assessments)
 - Reproductive endocrine labs for females under 55 years of age at consent
 - Endocrine
 - Hematology
 - Chemistry
- Assess and record any AEs and SAEs
- Collect eDiary device, review eDiary for compliance

6.5.11 *Early Termination*

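### Protocol v4.0 gives two answers on when early drug stoppers return the eDiary; a site following Table 2 loses Week 10 primary values that Table 3 would keep for mid-to-late stoppers

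*Protocol*

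**What the plan says.** All references are to protocol v4.0 and the current SAP.

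- **Table 2 (Appendix A).** The row "Dispense/collect eDiary" is marked at Screening, at Follow-up and at Early Treatment Discontinuation. Nothing is dispensed at the last two, so the mark there means collect.
- **Table 3 (Appendix A).** "An eDiary device is provided to subjects at the Screening visit and collected at the Follow-up visit". Its WI-NRS row runs daily to the Follow-up visit, whereas its dosing row ends when study drug stops.
- **Section 6.1.1.** Daily WI-NRS entry is required "throughout the screening, treatment, and follow-up periods".
- **Section 6.5.10.** The Follow-up visit list includes "Collect eDiary device, review eDiary for compliance". On timing: "The required Follow-up visit occurs 21 or 35 (+7 days) after the Week 10 visit or the last dose of study drug", the last-dose anchor being for subjects who stop early.
- **Section 5.6.** Subjects who stop drug before the end of treatment "will enter a 5-week follow-up period following the last dose of study drug".
- **Section 6.5.9.** Staff are to "inform subject to continue entering WI-NRS score until Follow-up visit". This instruction is written for the Week 10 visit only.
- **SAP 6.1.3 and 6.1.5.** Week 10 is the average over Study Days 64-70. At least four entries are needed; otherwise the week is imputed within treatment group.
- **SAP 6.4.1.** ITT includes every randomized subject who was dispensed drug.

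**The concern.** Stopping study drug is not the same as leaving the study. An early stopper still owes about five weeks of diary entries, and for many of them those weeks include Days 64-70, from which the primary endpoint is computed. If the site takes the device back at the discontinuation visit, those entries cannot be made and cannot be recovered later.

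Nothing else in the protocol settles the conflict for that visit. Section 6.5 has no subsection for Early Treatment Discontinuation; 6.5.11 covers withdrawal of consent and loss to follow-up. The Table 2 column is therefore the only list of what to do there. Footnote 7 of Table 2 points to Table 3, but it is attached to the eDiary review row, which has no mark in that column.

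Sites could reasonably act differently, so whether a stopper's primary value is observed or imputed would depend on which table the site read.

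**Working it through.** The plan states no expected rate of discontinuation or of missing Week 10 diaries, so there is no figure of its own to reproduce. The check is a day count.

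**Inputs.** Week 10 window Days 64-70 and a minimum of four entries (SAP 6.1.3). Follow-up visit at last dose + 35 days, up to + 42 with the window (Sections 5.6 and 6.5.10). The lag from last dose to the discontinuation visit is not stated; 0, 3 and 7 days are assumed.

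**Last day the device is needed.** If the device is last available on Study Day L, the possible Week 10 entries are max(0, min(7, L - 63)). Four entries require L - 63 ≥ 4, so L ≥ 67.

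**Earliest last-dose day d with an observable Week 10 value:**

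| Reading | L | Condition | First observable d |
|---|---|---|---|
| Table 2, visit on last-dose day | d | d ≥ 67 | Day 67 |
| Table 2, visit 3 days later | d + 3 | d ≥ 64 | Day 64 |
| Table 2, visit 7 days later | d + 7 | d ≥ 60 | Day 60 |
| Table 3, Follow-up at +35 | d + 35 | d ≥ 32 | Day 32 |
| Table 3, Follow-up at +42 | d + 42 | d ≥ 25 | Day 25 |

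**Where the choice of table matters.** With a same-day discontinuation visit, the affected last-dose days are Days 32-66 (66 - 32 + 1 = 35 days) or Days 25-66 (42 days). With a 7-day lag they are Days 32-59 (28 days) or Days 25-59 (35 days). Last doses up to Day 31 (+35) or Day 24 (+42) are unobservable under either table.

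**Who is affected.** SAP 6.1.5 and 6.7 define as non-responders those who stop for lack of efficacy or use an excluded therapy for worsening. Their primary outcome does not depend on the diary. Other stoppers, for example for an adverse event, are imputed within arm from baseline and weekly scores. Under Table 2 those scores are almost wholly on-drug.

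**Illustrative number of subjects.** In the Phase 2 PN study (protocol 1.5.3), 3 serlopitant and 6 placebo subjects stopped for treatment-emergent adverse events. The denominators are inferred from the reported percentages: 71.9% = 46/64 and 61.9% = 39/63. At 140 per arm:

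- serlopitant: 140 × 3/64 = 6.6
- placebo: 140 × 6/63 = 13.3
- total: 19.9 of 280 (7.1%)

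If stop days were uniform over Days 1-66 (assumption), those in the affected range with a same-day visit number 19.9 × 35/66 = 10.6 to 19.9 × 42/66 = 12.7, or about 11 to 13. With a 7-day lag the range is 19.9 × 28/66 = 8.4 to 19.9 × 35/66 = 10.6.

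**The case against.** The best defence is that the Table 2 mark is a slip that sites would read past. Table 2 marks the device for collection twice for the same subject, because its footnote 2 applies the Follow-up visit to early stoppers too. Its WI-NRS row has no mark at Follow-up even for completers, who plainly continue, so Table 2 is not a reliable guide to diary duration. Three other passages agree with one another. The mark may also have been meant for subjects who leave the study at that visit. All of this supports correcting Table 2 rather than Table 3, but it does not tell a site coordinator working from the column what to do.

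A second defence is that the plan already has a tipping point analysis over both arms (SAP 6.8.3), and that the imputation uses each subject's own scores. That is true, and it limits the consequence. It tests sensitivity to the missing values but does not supply them.

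Three stronger readings are tempting but unsupported:

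- **That Table 2 makes Week 10 unobservable for every early stopper.** This fails for stops late enough that the visit falls on or after Day 67, and the cut-off moves with the unstated visit lag.
- **That the SAP's post-treatment diary windows depend on early stoppers keeping the device.** The shell that reports them, Table 14.2.4.3, is limited to subjects with observed Week 10 data, and completers keep the device under either table.
- **That all 20 or so illustrative adverse-event stoppers are affected.** The earlier ones are lost whichever table is followed.

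**Conclusion.** The contradiction is real, is in current text, and should be reconciled. A site following Table 2 loses an observable Week 10 value for almost all early drug stoppers. Following Table 3 would preserve it for last doses from about Day 25-32 up to about Day 59-66, but does nothing for earlier stops. The effect is confined to subjects whose status is not already set by a non-responder rule.

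On the Phase 2 adverse-event stopping rates, uniform stop days and a same-day visit, about 11 to 13 adverse-event stoppers would fall in that range, somewhat fewer if the visit lags. Stops for other reasons outside the rules are not counted, because no rate is given for them.

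A reader might infer that the treatment comparison is biased. The documents do not support that: no discontinuation rate is stated for this trial, both arms are affected, and neither the size nor the direction of any effect can be derived. What is shown is avoidable, site-dependent loss of primary data within that range of stop days.

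**What to change.** In Table 2, remove the eDiary-collection mark at Early Treatment Discontinuation, except for subjects who leave the study at that visit. Add to the same column the Section 6.5.9 reminder to keep entering WI-NRS until Follow-up. Table 2 then agrees with Table 3, 6.1.1 and 6.5.10.

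The cost is one table mark and one line; the device and the Follow-up visit already exist. The change helps only subjects who have not yet passed the discontinuation visit. The downside is that some Days 64-70 scores will be off drug and may reflect itch therapies that Section 5.7.2 permits during follow-up.

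No SAP change is needed for this. SAP 6.1.3 and 6.1.5 already average the available Days 64-70 entries, with no on-treatment condition, and impute only weeks with fewer than four.

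Continuing diary entry to Day 70 when the Follow-up visit falls earlier is a separate, optional choice. It would add at most 70 - (1 + 35) = 34 diary days. It would also require extending concomitant-therapy recording, which Section 5.7 defines as therapies "used by a subject from initiation of study drug treatment through the follow-up period", and adjusting the end-of-study definition in Section 9.10, which is tied to the last visit.

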APPENDIX B LIST OF STRONG CYP3A4 INHIBITORS

The list of strong CYP3A4 inhibitors is based on the FDA list effective September 26, 2016, *Examples of clinical inhibitors for P450-mediated metabolisms (for concomitant use clinical DDI studies and/or drug labeling)* (“[Examples of clinical inhibitors for P450-mediated metabolisms \(for concomitant use clinical DDI studies and/or drug labeling \(9/26/2016\)\)](#)”).

Note: This Appendix may be replaced if applicable (e.g., if updated by the FDA) through site communications without requiring a protocol amendment.

1. boceprevir
2. clarithromycin
3. cobicistat
4. conivaptan
5. danoprevir and ritonavir
6. diltiazem
7. elvitegravir and ritonavir
8. idelalisib
9. indinavir and ritonavir
10. itraconazole^a
11. ketoconazole^a
12. lopinavir and ritonavir
13. nefazodone
14. nelfinavir
15. paritaprevir and ritonavir and (ombitasvir and/or dasabuvir)
16. posaconazole^a
17. ritonavir
18. saquinavir and ritonavir
19. telaprevir
20. tipranavir and ritonavir
21. troleandomycin
22. voriconazole^a
23. regular grapefruit juice consumption (note: The effect of grapefruit juice varies widely among brands and is concentration-, dose-, and preparation-dependent. Grapefruit juice may be a strong or a moderate CYP3A inhibitor depending on the preparation)^b

^a When administered topically, it may not be considered a strong CYP3A4 inhibitor due to limited systemic absorption.

^b The occasional consumption of grapefruit juice or the consumption of grapefruit or other citrus fruits (e.g., pomelo, lemon, lime, Seville orange, bitter orange, starfruit) is not contraindicated.

APPENDIX C WORST ITCH NUMERIC RATING SCALE QUESTIONNAIRE

NRS for Itch Intensity

CHECK THE NUMBER ON THE SCALE THAT CORRESPONDS WITH YOUR INTENSITY LEVEL

How would you rate your WORST itch in the past 24 hours, on a scale from 0 to 10, where 0 is No itch and 10 is Worst itch imaginable?

										
0	1	2	3	4	5	6	7	8	9	10
No Itch										Worst Itch Imaginable

APPENDIX D INVESTIGATOR’S GLOBAL ASSESSMENT OF PRURIGO NODULARIS: ACTIVITY AND STAGE

Score	Category	Description: Activity (IGA PN-A)
0	Clear	No nodules have excoriations or crusts
1	Almost Clear	Very small proportion of nodules have excoriations or crusts (up to approximately 10% of all nodules)
2	Mild	Minority of nodules have excoriations or crusts (approximately 11- 25% of all nodules)
3	Moderate	Many nodules have excoriations or crusts (approximately 26- 75% of all nodules)
4	Severe	Majority of nodules have excoriations or crusts (approximately 76-100% of all nodules)

Score	Category	Description: Stage (IGA PN-S)
0	Clear	No nodules (0 nodules)
1	Almost Clear	Rare, flattened lesions, with no more than 5 dome-shaped palpable nodules (approximately 1-5 nodules)
2	Mild	Few, mostly flattened lesions, with small number of dome-shaped palpable nodules (approximately 6-19 nodules)
3	Moderate	Many lesions, partially flattened, and dome-shaped palpable nodules (approximately 20-100 nodules)
4	Severe	Abundant lesions, majority are dome-shaped palpable nodules (over 100 nodules)

